3.0 Change: *Number Cases*

[name]

Previous language: Cases will be enrolled until 326 cases have received the Secur-Fit Advanced Hip Stem.

New language: Cases will be enrolled until 314 cases have received the Secur-Fit Advanced Hip Stem.

Rationale for Change: Reduction of cases to 314 poses no risk to the statistical analysis and demonstration of long-term safety and effectiveness of the Secur-Fit Advanced Hip Stem.

Change: Primary Objective

Previous language: To evaluate and determine the success rate, defined as absence of stem revision for aseptic loosening or femoral fracture, at 5 years postoperative with the Secur-Fit Advanced Hip Stem.

New language: To evaluate and determine the success rate, defined as absence of stem revision for aseptic loosening or device-related femoral fracture, at 5 years postoperative with the Secur-Fit Advanced Hip Stem.

Rationale for Change: Clarification that femoral fractures which are unrelated to the study device will not be included in primary analysis.

Change: Secondary Objective

Previous language: To evaluate rate of femoral fracture among patients implanted with the Secur-Fit Advanced Hip Stem within 30 days postoperative, and compare with rates reported for other primary hip stems in the literature.

New language: To evaluate rate of device-related femoral fracture among patients implanted with the Secur-Fit Advanced Hip Stem within 30 days postoperative, and compare with rates reported for other primary hip stems in the literature

Version	Description	Changed By
	Rationale for Change: Clarification that femoral fractures	
	which are unrelated to the study device will not be included	
	in the secondary endpoint evaluation.	
	Change: Secondary Objective	
	Previous language: To demonstrate that surgeons can use	
	the Secur-Fit Advanced Hip Stem to consistently match a	
	preoperative plan for femoral head center, offset and leg	
	length postoperatively.	
	New language: [Removal of endpoint]	
	Rationale for Change: This secondary objective is no longer	
	required to support Stryker's business needs, and removal	
	does not affect safety or performance.	

Table of Contents

S	STUDY SYNOPSIS2					
E	VALUA	FION SCHEDULE	8			
1	INT	RODUCTION	9			
	1.1 1.2 1.3 1.4	BACKGROUND STUDY DEVICE PRECLINICAL DATA CLINICAL DATA TO DATE	10			
2	STU	DY OBJECTIVES	12			
	2.1 2.1.1 2.1.2 2.1.3 2.2	Secondary	12 12 12			
3	CLI	NICAL STUDY PLAN	14			

Appendix H Product Labeling

List of Figures and Tables

Figure 1: Secur-Fit Advanced A/P View	18
Table 1: Secur-Fit Advanced Stem Offsets	19
Table 2: Femoral Head Compatibility	20
Table 3: Secur-Fit Advanced Compatible Acetabular Components	21

List of Abbreviations

ADE Adverse Device Effect

AE Adverse Event
AP Anteroposterior
BMI Body Mass Index

CFR Code of Federal Regulations

CP Commercially Pure

CSM Clinical Study Manager

DCR Data Clarification Request

EC Ethics Committee

eCRF Electronic Case Report Form

EDC Electronic Data Capture

GCP International Conference of Harmonisation Good Clinical Practice

HA Hydroxylapatite
HHS Harris Hip Score

HIPAA Health Insurance Portability and Accountability Act
ICMJE International Committee of Medical Journal Editors

IRB Institutional Review Board

LEAS Lower Extremity Activity Scale

PER Product Experience Report

PI Principal Investigator

QOL Quality of Life
ROM Range of Motion

SAE Serious Adverse Event

SC Study Coordinator

SF-12 Short Form-12

THA Total Hip Arthroplasty

UADE Unanticipated Adverse Device Effect

UHMWPE Ultra High Molecular Weight Polyethylene

Study Synopsis

Title	A prospective, post-market, multi-center evaluation of the clinical outcomes of the Secur-Fit Advanced Hip Stem					
Short Title	Secur-Fit Advanced Outcomes Study					
Protocol Number	75					
Туре	Post-market					
Methodology	This study is a prospective, open-label, post-market, non-randomized, multi-center clinical evaluation of the Secur-Fit Advanced Hip Stem for primary total hip arthroplasty (THA) with a cementless application in a consecutive series of patients who meet the eligibility criteria. The total enrollment goal for the study is 314 cases, all of which will receive the Secur-Fit Advanced Hip Stem.					
Study Duration	 Follow-up of each primary THA case to 10 years Enrollment period of 24 months Approximate 12-year total duration 					
Study Center(s)	5 to 8 investigational centers					
Hypothesis	The success rate of the Secur-Fit Advanced femoral stem, defined as absence of stem revision for aseptic loosening or device-related femoral fracture, is no worse than 99% at 5 years postoperative with a non-inferiority margin of 2.5%.					

Primary:

 To evaluate and determine the success rate, defined as absence of stem revision for aseptic loosening or device-related femoral fracture, at 5 years postoperative with the Secur-Fit Advanced Hip Stem.

Secondary:

Objectives

- To evaluate all-cause revision and removal rates with the Secur-Fit Advanced Hip Stem and compare with those reported for other primary hip stems in the literature.
- To evaluate rate of device-related femoral fracture among patients implanted with the Secur-Fit Advanced Hip Stem within 30 days postoperative, and compare with rates reported for other primary hip stems in the literature.
- To demonstrate the close relationship between the seating height of the Secur-Fit Advanced Hip Stem and its associated femoral broach.

	Function and health related quality of life (QOL) will be compared between the Securifit Advanced Him Stem and published results.			
	between the Secur-Fit Advanced Hip Stem and published results for other primary hip systems, the following outcomes measures will be collected:			
	○ Harris Hip Score (HHS)			
	○ Short Form-12 (SF-12)			
	 Lower Extremity Activity Scale (LEAS) 			
Additional Data	∘ EQ-5D			
Collection	 1-year, 2-year and 5-year SF-12,LEAS and HHS will be presented with respect to improvement from preoperative scores. EQ-5D data will be summarized and presented. An additional Follow-up Questionnaire will be administered annually in postoperative years 3, 4 and 6-10 to assess patient satisfaction and pain, and to capture adverse events. 			
	Radiographic stability and complications will be compared between those implanted with the Secur-Fit Advanced Hip Stem and published results for other primary hip systems.			
Number of Cases	Cases will be enrolled until 314 cases have received the Secur-Fit Advanced Hip Stem.			

Inclusions:

- A. Patient has signed an IRB/EC approved, study specific Informed Patient Consent Form.
- B. Patient is a male or non-pregnant female, skeletally mature and age 21-75 years at time of study device implantation.
- C. Patient has a diagnosis of Non-Inflammatory Degenerative Joint Disease.
- D. Patient is a candidate for primary total hip arthroplasty.
- E. Patient is willing and able to comply with postoperative scheduled clinical and radiographic evaluations and rehabilitation.

Exclusions:

- F. Patient has previously undergone open surgical intervention on the operative hip.
- G. Patient has a prior femoral fracture, with or without deformity, on the operative side.
- H. Patient has an existing total hip replacement on the contralateral side.
- I. Patient requires simultaneous bilateral total hip replacement.
- J. Patient has a Body Mass Index (BMI) > 45.
- K. Patient has an active or suspected latent infection in or about the affected hip joint at time of study device implantation.
- L. Patient has a neuromuscular or neurosensory deficiency that would create an unacceptable risk of instability, prosthesis fixation failure or complications in postoperative care, or which limits the ability to evaluate the safety and efficacy of the device.

Inclusion/Exclusion Criteria

Exclusions (continued): M. Patient has bone stock that is inadequate for support or fixation of the prosthesis, or is diagnosed with a systemic disease (e.g. Lupus Erythematosus) or a metabolic disorder (e.g. Paget's Inclusion/Exclusion disease) leading to progressive bone deterioration. Criteria N. Patient is immunologically suppressed or receiving steroids in excess of normal physiological requirements (e.g. > 30 days). O. Patient has a known sensitivity to device materials. P. Patient is a prisoner. **Secur-Fit Advanced Hip Stem** Required Components: Secur-Fit Advanced Femoral Stem The femoral component must be used in a cementless application. Stryker acetabular components and femoral bearing heads must be **Study Device** used according to this study protocol. The following ancillary devices are permissible: Compatible Stryker femoral bearing heads Compatible Stryker acetabular shells, liners and inserts The compatible Stryker head and acetabular components are listed in the surgical protocol.

Primary Objective:

5-year success rate of the Secur-Fit Advanced Hip Stem with an endpoint of revision for aseptic loosening or device-related femoral fracture will be compared with a 99% success rate, with a 2.5% noninferiority margin.

Statistical Methodology

Secondary Objectives:

- The Kaplan-Meier survival curve of revision/removal for the Secur-Fit Advanced Hip Stem will be displayed.
- The rate of device-related femoral fracture within 30 days of index THA will be reported.
- The mean amount of unintended exposure or countersink of the femoral component upon final seating will be presented.

Evaluation Schedule

Evaluation	Preop X-rays (-1 yr) CRFs (-4 mos)	Intraop	6 weeks (+ 3 wks)	1 year (+ 2 mos)	2 years (+ 2 mos)	3 years (+ 3 mos)	4 years (+ 4 mos)	5 years (+ 4 mos)	6 years (+ 4 mos)	7 years (+ 4 mos)	8 years (+ 4 mos)	9 years (+ 4 mos)	10 years (+ 4 mos)
Inclusion/ Exclusion	x												
Demographics & Medical History	х												
Preoperative Functional Evaluation	x												
Preoperative Digital Template	s												
Surgical Details		Х											
Postoperative Functional Evaluation			x	x	x			x		Optional			Optional
SF-12	X		X	Х	Х	Х	X	X		Optional			Optional
LEAS	Х		Х	Х	Х	Х	Х	Х		Optional			Optional
EQ-5D	Х		Х	Х	Х	Х	Х	Х		Optional			Optional
Lauenstein lateral and anteroposterior (AP) pelvis radiographs	x		x	x	x			x		Optional			Optional
Follow-up Questionnaire			As needed	As needed	As needed	x	х	As needed	x	x	х	х	х

X: Evaluation is required for all cases.

Functional Evaluation: The Functional Evaluations include the HHS, a subjective outcomes tool completed by the investigator that measures function, pain and motion.

SF-12: The SF-12 is a 12 item patient questionnaire that evaluates general health and well-being.

LEAS: The LEAS is a self-administered patient evaluation designed to reflect patient activity.

EQ-5D: The EQ-5D is a standardized instrument for use as a measure of health outcome.

Follow-up Questionnaire: The Follow-up Questionnaire is a short patient questionnaire intended to provide information on dislocation, patient satisfaction, pain and whether or not there have been any revisions or removals of the study device since the last follow-up visit.

S: Templating and preoperative plan will be collected for a subset of patients at select sites.

1 Introduction

This document is a protocol for a human research study. This study will be conducted in compliance with the protocol, Good Clinical Practice (GCP) Standards, associated Federal regulations and all applicable research requirements.

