2.1.2 Secondary

The secondary objectives of this study will include evaluation of all-cause revision and removal rates with the Secur-Fit Advanced Hip Stem and comparison with those reported for other primary hip systems in the literature.

Additionally, the rate of device-related femoral fracture among patients implanted with the Secur-Fit Advanced Hip Stem within 30 days postoperative will be evaluated and compared with rates reported for other primary hip stems in the literature.

The close relationship between the seating height of the Secur-Fit Advanced Hip Stem and its associated femoral broach will also be demonstrated by intraoperatively measuring the component exposure or countersink upon final seating.

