9.1.3 Primary Efficacy Analysis

The primary hypothesis to be tested will be that the success rate at 5 years postoperative with the Secur-Fit Advanced Hip Stem is not worse than 99% with a non-inferiority margin of 2.5%.

That is, the following hypothesis will be tested:

Ho: Pt <= 99% - 2.5% HA: Pt > 99% - 2.5%

Here, Pt is the success rate at 5 years postoperative with the Secur-Fit Advanced Hip Stem

A 90% two-sided confidence interval will be computed for the success rate at 5 years. If the lower bound of the confidence interval is greater than 96.5%, then the non-inferiority hypothesis will be supported.

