9.1.4 Secondary Efficacy Analysis

The all-cause revision and/or removal rates of the Secur-Fit Advanced Hip Stem will be reported.

The rate of device-related femoral fracture among patients implanted with the Secur-Fit Advanced Hip Stem within 30 days postoperative will be evaluated.

The mean amount of unintended exposure or countersink of the femoral component upon final seating will be presented; standard deviation, median, minimum, and maximum will be displayed.

The analysis for the additional data collection is in 9.4.1 Data Summary.

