9.4 Statistical Methodology

9.4.1 Data Summary

Descriptive statistics will be computed for all baseline conditions and demographic parameters. That is, for continuous data, the N, mean, median, standard deviation, minimum and maximum will be computed. For categorical data, the frequency will be computed. The data will be presented by appropriate subgroups (e.g., center, gender).

A Kaplan-Meier survivorship curve will be displayed for revision and/or removal of the Secur-Fit Advanced Hip Stem for aseptic loosening or device-related femoral fracture.

A Kaplan-Meier survivorship curve will be displayed for all-cause revision and/or removal of the Secur-Fit Advanced Hip Stem.

For the additional data collected according to Section 2.1.3, data will be summarized according to visit. For parameters represented by continuous variables (e.g., ROM), the

summaries will consist of the N, mean, median, standard deviation, minimum, and maximum values. For categorical variables (e.g., Mobility from EQ-5D), the frequency and percentage in each category will be presented. A paired t-test will be performed to evaluate the change in clinical and patient outcomes, preoperative to 5 years within the Secur-Fit Advanced Hip Stem. The 1-year, 2-year and 5-year SF-12, LEAS and HHS will be presented with respect to improvement from preoperative scores.

For the Follow-up Questionnaire, frequency and percentage will be computed for each category according to visits. Applicable lists based on Follow-up Questionnaire will be generated to capture AEs.

For radiographic data, data will be presented according to visits for available parameters. Frequency and percentage will be computed for radiolucency according to visit. Lists will be generated for migration over time. Radiographic failure will be evaluated, where radiographic failure is defined as subsidence of greater than 5 mm, migration of greater than 5° in any direction or at least 2 mm radiolucency in all zones within a single view.

Documentation of statistical analyses utilizing SAS® software version 9.1.3 or higher.

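### Two of the three secondary objectives promise a comparison with published rates, but the planned analyses give a rate and a curve with no confidence interval

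*Combined protocol and SAP*

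**What the plan says.** **Objectives.** In the Study Synopsis, one secondary objective is to evaluate all-cause revision and removal rates and "compare with those reported for other primary hip stems in the literature". Another is to evaluate 30-day device-related femoral fracture and "compare with rates reported for other primary hip stems in the literature". Section 2.1.2 repeats both; the fracture rate "will be evaluated and compared with rates reported for other primary hip stems in the literature". The third secondary objective, seating height relative to the broach, promises no literature comparison.

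**Planned analyses.**
- Synopsis, Statistical Methodology: "The Kaplan-Meier survival curve of revision/removal for the Secur-Fit Advanced Hip Stem will be displayed" and "The rate of device-related femoral fracture within 30 days of index THA will be reported".
- Section 9.1.4: "The all-cause revision and/or removal rates of the Secur-Fit Advanced Hip Stem will be reported". The 30-day fracture rate is to be evaluated, with nothing further specified. Seating height gets a mean, standard deviation, median, minimum and maximum.
- Section 9.4.1: "A Kaplan-Meier survivorship curve will be displayed for all-cause revision and/or removal of the Secur-Fit Advanced Hip Stem". No time point, interval or band is mentioned.

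**The one planned interval** is for the primary endpoint, in Section 9.1.3: "A 90% two-sided confidence interval will be computed for the success rate at 5 years".

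**Population.** Section 9.4.4 bases the primary and secondary efficacy analyses on non-censored subjects who received the stem and are available for efficacy evaluation.

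**The concern.** The objectives call for a comparison; the analysis text stops at description. Followed as written, the report would set an observed percentage beside a published one without showing how far the observed percentage could move by chance. If events are few, that movement is large relative to the rate. A reader could then take a stem with twice the published risk to be in line with the literature, or take a low count as evidence of a lower risk when the data do not show it. Section 12.5 describes the study as informing clinicians by setting this device against published results for similar ones, so the comparison matters to its stated purpose.

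**Working it through.** **The plan's own figure.** The documents state no sample size, rate or precision for the secondary comparisons. The only figure is for the primary test (Section 9.4.2), and it reproduces. With p0 = 0.965, p1 = 0.99, one-sided alpha 0.05 and power 0.80:

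n = [1.645 × √(0.965 × 0.035) + 0.842 × √(0.99 × 0.01)]² / 0.025² = 238.4

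With continuity correction, (n/4) × [1 + √(1 + 2/(0.025 n))]² = 277, and 277 / 0.85 = 326. The primary calculation is not in question here.

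**Inputs for the secondary rates.** N = 314 implanted cases (Section 3.3). The event counts and true rates below are assumptions.

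**Expected events = 314 × rate.** A true rate of 0.5% gives 1.6, 1% gives 3.1, 2% gives 6.3 and 3% gives 9.4.

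**Exact (Clopper-Pearson) 95% interval** for x events in n: the lower limit is the 0.025 quantile of Beta(x, n − x + 1), and the upper limit is the 0.975 quantile of Beta(x + 1, n − x). For x = 0 the upper limit is 1 − 0.025^(1/314) = 1.17%.

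| Events in 314 | Rate | Exact 95% interval |
|---|---|---|
| 0 | 0% | 0 to 1.17% |
| 1 | 0.32% | 0.01 to 1.76% |
| 3 | 0.96% | 0.20 to 2.77% |
| 6 | 1.91% | 0.70 to 4.11% |
| 10 | 3.18% | 1.54 to 5.78% |

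The ratio of upper to lower limit is about 14 at 3 events (2.77/0.20), about 6 at 6 events (4.11/0.70) and about 4 at 10 events (5.78/1.54).

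**What a bare rate could hide.**
- Published rate 1%, true rate 2%: the study shows 3 or fewer events, so an observed rate below 1%, with probability P(X ≤ 3 | 314, 0.02) = 12.5%.
- Published rate 0.5%, true rate 1%: P(X ≤ 1 | 314, 0.01) = 17.8%.
- Published rate 1%: even zero events does not show a lower rate at one-sided 0.025, because 0.99^314 = 0.043.
- Published rate 2%, true rate 1%: the interval lies wholly below 2% only with 0 or 1 event (upper limit 1.76%; with 2 events it is 2.28%). That also has probability 17.8%.

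**Revision/removal over years.** The table treats every case as fully followed. Applying the plan's 15% loss assumption to 314 leaves 314 × 0.85 = 266.9, or 267. Six events in 267 give 0.83 to 4.83%, and ten give 1.81 to 6.78%. A Kaplan-Meier estimate handles the loss properly, but only if cases lost without revision stay in the risk set until they are censored. Restricting to non-censored subjects, as Section 9.4.4 literally reads, removes them.

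**The case against.** These are descriptive secondary endpoints in a single-arm post-market study. The one formal hypothesis has its interval and its decision rule. Saying that a curve will be displayed does not exclude bands, and a statistician might add intervals unprompted. All of that is fair and keeps the point modest. Even so, nothing in the plan requires an interval where a comparison is promised.

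Three stronger readings are tempting, and the documents do not support them:
- *The plan intends to claim a lower or better rate.* It does not say so. The expectation of comparable rates, in Section 2.2, concerns adverse events, not these two endpoints. The risk of misreading depends on how the results are later worded.
- *Only a handful of events is expected.* No fracture or all-cause revision rate is given. Small counts follow from assumed rates up to about 2%; all-cause revision over 10 years could yield more, and the relative uncertainty would then be smaller.
- *All the secondary objectives are affected.* Seating height promises no comparison and has its own summary statistics.

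Two cautions about the remedy stand. Log-log bands on a curve drawn from non-censored subjects would put precise-looking limits on a distorted estimate. And an interval around the study rate still treats the published rate as exact and does not settle which published rate is used; no source or reference value is named for either endpoint.

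**Conclusion.** The point holds for two endpoints: all-cause stem revision/removal and 30-day device-related femoral fracture. Their objectives promise comparison with the literature, and the analyses supply no measure of precision. The size depends on assumed counts. With all 314 cases evaluable, 0, 3 and 10 events give exact 95% intervals of 0 to 1.17%, 0.20 to 2.77% and 1.54 to 5.78%, too wide for the rate alone to carry a comparison. This is a worthwhile and inexpensive improvement to the reporting. It should not be read as a flaw in the sample size, the primary non-inferiority analysis or the seating-height objective.

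**What to change.** In the synopsis and Section 9.1.4, with Section 9.4.1 brought into line:

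1. Report the 30-day device-related femoral fracture rate with an exact (Clopper-Pearson) two-sided 95% interval.
2. Report all-cause stem revision/removal as Kaplan-Meier estimates at 5 and 10 years with log-log 95% intervals, and draw the bands on the curve. Compute them in all implanted cases, with censored cases contributing follow-up until censoring, and state that the non-censored population of Section 9.4.4 does not apply to this analysis.
3. If comparison wording is used, make it symmetric: *lower* only if the whole interval lies below the published rate, *higher* if it lies wholly above, otherwise *not distinguishable*. The *higher* branch is needed: 10 fractures in 314 (1.54 to 5.78%) against an assumed published 1% lies wholly above it, and a rule with only a *lower* branch would call that inconclusive.

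The cost is a few sentences in the synopsis and Section 9, including the population statement, plus standard software output. Sample size, visits and data collection do not change. The downside is that some comparisons will read as inconclusive.

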2.1.3 Additional Data Collection

Clinical Outcomes:

Clinical outcomes will be evaluated with the total HHS, including pain, motion and function, preoperatively and at the 6-week, 1, 2 and 5-year visits. Additional HHS data will be obtained at the 7-year and 10-year time points at investigational sites that choose to bring their subjects in for these optional visits.

Patient Outcomes:

Pain, function and health related QOL will be compared between the Secur-Fit Advanced Hip Stem and reports in the literature for other primary femoral stems on the market. The SF-12 is a 12 item patient self-assessment evaluating health and general well-being. The LEAS is a tool that has been developed and validated to evaluate the level of patient activity. The EQ-5D is a standardized instrument for use as a measure of health outcome. These tools will be used to assess patient health-related QOL and will be collected preoperatively and at the 6-week, 1, 2, 3, 4, and 5-year time points.

A Follow-up Questionnaire will be administered annually in postoperative years 3, 4 and 6-10 to assess patient satisfaction and pain, and to capture AEs. This questionnaire, which will also be completed during each interval through 5 years postoperative at which the subject is not seen by the investigator, will provide the information necessary to create an accurate Kaplan-Meier Survival Curve. Patient outcomes data will also be obtained at the 7-year and 10-year time points at investigational sites that choose to bring their subjects back in for these optional visits, in addition to the required Follow-up Questionnaire described.

Radiographic Outcomes:

To assess radiographic stability as compared with other primary femoral stems, radiographs will be taken and collected in the low AP pelvis and Lauenstein lateral views for the preoperative, 6-week, 1, 2 and 5-year intervals. Additional radiographs will be obtained at the 7-year and 10-year time points at investigational sites that choose to bring their subjects back in for these optional visits.

The low AP pelvis view allows for measurement of the position of the hip center, femoral offset and neck angle, and any leg length discrepancy. The Lauenstein lateral view allows for evaluation of the entire hip joint as well as the femoral head, neck and proximal shaft. Suggested radiographic technique for the views required is included in Appendix C.

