7.4 Annual Follow-up Visits

Clinical data will be collected via office visit by the investigator at the following annual

postoperative intervals: 1-year, 2-year and 5-year. Tools for postoperative evaluation at each of

these intervals will be the HHS, AP pelvis and Lauenstein lateral radiographs. In the event that

an in-person visit cannot be conducted and radiographs cannot be obtained, a Follow-up

Questionnaire will be completed via mail, online completion (if available), or telephone interview

with the subject by investigative site personnel.

Patient outcomes data will also be collected with the Follow-up Questionnaire, SF-12, LEAS, and

EQ-5D patient questionnaires at each office visit and at the 3-year and 4-year intervals via mail

or online completion, if available.

All clinical data, radiographs, and patient outcomes data must be collected within ± 2 months of

the 1-year and 2-year anniversary dates. For remaining annual time points, the window expands

to ± 3 months of the 3-year anniversary date and ± 4 months of the 4-year through

10-year anniversary dates.

The initial phase of the study will continue for 5 years after surgery and include collection of the previously described radiographs, HHS, SF-12, LEAS and EQ-5D patient questionnaires. In the second phase of the study, all subjects will complete a brief Follow-up Questionnaire annually at the 6-year, 7-year, 8-year, 9-year and 10-year follow-up intervals. This form may be completed by the SC during a subject telephone interview, or by the subject either at home or during a clinic visit. The questionnaire will be used to obtain the following information, at a minimum:

- Subject satisfaction with the hip replacement
- Presence of any pain in the study hip
- Any surgeries performed on the study hip

The questionnaire will also provide information on any revisions and enable calculation of the Kaplan-Meier Survival Curve.

Additionally, at investigational sites that choose to continue collecting clinical and radiographic data during the second phase of the study, subjects will be evaluated again at 7 and 10 years after surgery.

8 Adverse Events

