8.1 Reporting of Adverse Events

The AE reporting requirements for this study are as follows:

- All AEs that meet the definition of serious and occur within the perioperative period (intraoperative to hospital discharge)
- All AEs related to the operative site, regardless of seriousness or time of occurrence

On postoperative functional evaluations, investigators and SCs will be prompted to question subjects as to whether they have seen a doctor for any reason, been hospitalized for any reason or have a current impediment to their function.

Additionally, SCs will be responsible for following up with the subjects regarding any questionable responses received on the Follow-up Questionnaire administered in postoperative years 6

through 10. If it is determined upon this further investigation that a protocol-defined AE has occurred, the SC will be responsible for completing an AE eCRF, submitting the event to Stryker and reporting to the IRB/EC, as required.

The following decision tree facilitates identification of AEs for which reporting is required under this study protocol:

[figure not shown]

Figure 4. Adverse Event Decision Tree

General Physical Examination Findings

At screening for inclusion into the study, any clinically significant abnormality should be recorded as a preexisting condition and reported on the Demographics eCRF. From the time of consent forward, any new clinically significant findings or abnormalities that meet the definition of a protocol defined AE must also be recorded and documented as an AE.

Adverse Event Reporting Period

The study period during which AEs must be reported is normally defined as the period from the initiation of any study procedures to the end of the study treatment follow-up. The start of study procedures is considered to be the point of consent. Any AEs which fit the protocol defined reportable events must be reported from the time of consent until study completion.

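### The Follow-up Questionnaire is described unevenly, and neither itemised description asks directly about operative-site adverse events treated without hip surgery, so these may be under-captured in years 3, 4 and 6-10

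*Combined protocol and SAP*

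**What the plan says.** Content and purpose of the form:

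- Evaluation Schedule, footnote: the form is "intended to provide information on dislocation, patient satisfaction, pain and whether or not there have been any revisions or removals of the study device".
- Section 7.4, written for the second phase (years 6-10): the list opens with "The questionnaire will be used to obtain the following information, at a minimum" and names satisfaction, pain and "Any surgeries performed on the study hip". It adds that the form will supply information on revisions. Dislocation is not listed.
- Synopsis, Additional Data Collection: the form is used "to assess patient satisfaction and pain, and to capture adverse events". Section 2.1.3 says nearly the same, "to assess patient satisfaction and pain, and to capture AEs", and Section 9.4.1 builds AE listings from it.

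What must be captured, and how:

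- Section 8.1 makes reportable "All AEs related to the operative site, regardless of seriousness or time of occurrence".
- Under Section 8.1, the postoperative functional evaluations prompt staff to ask subjects "whether they have seen a doctor for any reason, been hospitalized for any reason or have a current impediment to their function".
- Section 8.1 also has coordinators follow up questionable answers on the questionnaire, but names only years 6 through 10.
- Still in Section 8.1, the investigator must ask specifically about AEs at each contact.

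How the form is completed (Sections 7.3 and 7.4): by mail or online at years 3 and 4; by coordinator telephone interview, at home or in clinic at years 6-10; by mail, online or telephone when a 6-week, 1-, 2- or 5-year visit is missed.

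**The concern.** Section 8.1 sets a wide net for operative-site AEs, with no limit on seriousness or time. For most of the ten years the required instrument is a short form whose stated items are much narrower. The open prompts that would pick up an infection treated with antibiotics, or a fracture managed without an operation, belong to a different instrument that is mostly not scheduled in those years.

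At stake are the AE tabulation (Section 9.2.2), the AE listings drawn from the form (Section 9.4.1), and the comparison of complication rates with published rates (Sections 2.2 and 12.3). Events that are not elicited can only lower the study's own rate. Dislocation and reoperation counts could also depend on which description the form follows.

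**Working it through.** The plan states no figure on this point, so the check is a comparison of passages.

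**Step 1. Which events each description asks about directly**

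| Event | Evaluation Schedule footnote | Section 7.4 minimum list | Section 8.1 open prompts |
|---|---|---|---|
| Stem revision or removal | Yes | Yes | Yes |
| Dislocation reduced without surgery | Yes | Not listed | Yes |
| Head or cup reoperation, stem retained | Not listed, if the study device means the stem | Yes | Yes |
| Infection treated without hip surgery | Not listed | Not listed | Yes |
| Femoral fracture treated without surgery | Not listed | Not listed | Yes |

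On the third row, the synopsis lists heads and acetabular parts as ancillary devices. Section 10.3 ends participation on revision of the study device but not on revision of a head or acetabular component. Both favour reading the term as the stem, but the synopsis places all of these parts in its Study Device row, so the reading is not certain.

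Infection and fracture are among the expected complications in Section 12.3.

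**Step 2. Where the open prompts and the call-back apply**

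| Time point | Required contact | Open prompts | Call-back stated in 8.1 |
|---|---|---|---|
| 6 weeks, years 1, 2, 5, attended | Functional evaluation | Yes | Not needed |
| Same visits, missed | Questionnaire | No | No |
| Years 3, 4 | Questionnaire, SF-12, LEAS, EQ-5D | No | No |
| Years 6, 8, 9 | Questionnaire | No | Questionable answers only |
| Years 7, 10 | Questionnaire; functional evaluation optional by site | Only at sites that choose it | Questionable answers only |

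The questionnaire is required without a required functional evaluation at years 3, 4, 6, 7, 8, 9 and 10, which is 7 of 10 annual time points. The stretches with no required functional evaluation run from year 2 to year 5 and from year 5 to year 10. The SF-12, LEAS and EQ-5D at years 3 and 4 are general health and activity measures, not AE instruments.

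**Step 3. Whether the other routes close the gap**

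- Questioning at each contact needs a questioner. A mailed, online or home-completed form need not have one.
- The call-back depends on a questionable answer to an item that was asked, and it is not stated for years 3 and 4 or for missed visits.
- Pain is in both itemised descriptions and may lead to a call-back. An event that has resolved may leave no pain to report.
- The year-5 evaluation carries the open prompts and can recover some events from years 3 and 4. No later required evaluation does this for years 6-10.

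**Step 4. Which endpoints are touched**

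Stem revision or removal is covered by both itemised descriptions, and the 30-day fracture rate is complete long before year 3. The effect is confined to the AE summaries and the comparison with published complication rates.

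**Step 5. Whether a size can be given**

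The 15% loss in Section 9.4.2 applied to 314 cases leaves 314 × 0.85 = 266.9, or about 267, at year 5. With no further loss, years 6-10 hold 5 × 267 = 1,335 subject-years. Turning that into a number of events needs a rate of non-surgical operative-site AEs and the share that no route picks up. The documents give neither.

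**The case against.** The strongest reply is that the descriptions are compatible. Section 7.4 states a minimum, the footnote states what the form is meant to inform, and the other sections state its purpose, so one form could satisfy all of them. The form itself may be specified in the eCRF appendix, which is not in the text reviewed, and it may already ask more. This stands. A reader might infer that the passages contradict one another, but a non-exhaustive list that omits dislocation does not contradict one that includes it.

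A reader might also infer that non-surgical complications are missed outright. The documents do not show that. Questioning is required at each contact, telephone completion is allowed in some years, pain can prompt a call-back in years 6-10, the year-5 visit looks back, and some sites will run year-7 and year-10 evaluations. Section 8.3 also requires 24-hour notice of any reoperation or component revision once the site knows of it. These routes reduce the risk but do not remove it, for the reasons in step 3.

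Finally, AEs are only tabulated, with no threshold or test, and the published comparators may have been collected no more fully. Both points are fair and limit the consequence. Incomplete capture would still lower this study's own rates; how far that flatters the device depends on the comparators, which the documents do not describe.

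**Conclusion.** The point holds as a risk of under-capture together with uneven wording. As written, the plan requires every operative-site AE at any time. At 7 of 10 annual time points it relies on a form whose stated items are narrow, which can be completed with no questioner present, and whose call-back is conditional and does not extend to years 3 and 4. Any resulting bias in the AE rates is downward.

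This rests on the form following the stated descriptions. If it already asks the broader questions, only the wording is at issue. A reader might go on to infer a particular number of lost events; any such count would rest on assumed rates and on no event being recovered by another route, so none is given. Nor do the documents support inferring a threat to the efficacy results: the primary endpoint, all-cause stem revision and the 30-day fracture rate are unaffected. It is worth correcting because the remedy is cheap.

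**What to change.** 1. Use one content list for the questionnaire in the synopsis, the Evaluation Schedule, Section 2.1.3 and Section 7.4: satisfaction, pain, dislocation, and any surgery on the study hip involving any component.
2. Add to the form the three prompts already used on functional evaluations in Section 8.1: doctor seen, hospitalized, impediment to function.
3. State in Section 8.1 that any positive answer triggers the coordinator call-back whenever the form is used, including years 3 and 4 and missed visits.

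If the form already contains these items, align the wording and extend the call-back statement.

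The cost is a slightly longer form, more call-backs, and IRB/EC notification of the revised form. No extra visits or staff are needed. Section 9.4.2 treats enrollment as finished at 314 cases, so new items would start during follow-up and ascertainment would differ before and after the change. That should be noted when AE rates are reported.
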